The current research specifically aims to examine the role of relief during extinction learning and to test whether positive-focused rehearsal exercise may be implemented to improve treatment outcomes in exposure therapy in a population of individuals who demonstrate excessive fear of public speaking. This is a highly relevant population, given that the National Comorbidity Survey Replication estimated that 13% of Americans are estimated to experience social phobia at some point in their lives (Kessler et al., 2012). Further, a more recent study assessed over 1100 college students and 63.9% reported a fear of public speaking (Ferreira Marinho et al., 2017). The current study has three primary aims. First, the study seeks to examine whether baseline reward sensitivity and positive affect predict relief following exposure. Second, the study seeks to examine whether relief predicts subsequent extinction learning across exposure trials. Third, the study seeks to test the efficacy of a positive rehearsal exercise following exposure, characterized by technology-guided recall and rehearsal of positively-valenced emotional aspects of speech exposures done in session, relative to a neutral rehearsal exercise following exposure, characterized by technology-guided recall and rehearsal of non-emotional, factual aspects of speech exposures done in session.

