Participants will complete rehearsal exercises after every two exposures to ensure there is sufficient content for rehearsal. Learning rate (change in expectancy of an aversive outcome across exposure trials) and relief rate (change in relief ratings across exposure trials) will be calculated based on self-reported expectancy and relief ratings provided after each exposure. We hypothesize that regardless of rehearsal group assignment, participants with reduced baseline reward sensitivity and positive affect will exhibit a slower relief rate relative to individuals with elevated baseline reward sensitivity and positive affect, and that lower positive affect will be associated with lower subsequent relief ratings relative to higher positive affect. We hypothesize that regardless of group assignment, higher relief ratings after the first exposure will be associated with a faster learning rate on subsequent exposure trials. Finally, we hypothesize that the positive rehearsal group will lead to significantly greater reductions in symptoms of social phobia and greater increases in reward sensitivity and positive affect at the end of the study, as well as faster learning and relief rates relative to the neutral rehearsal group.

Research Design & Methods:

Visits will either be conducted over HIPAA-compliant video conferencing platform Zoom or in person.

OVERVIEW

The experiment will consist of two study visits. Visit 1 will include informed consent and questionnaires. Participants will then complete a series of short 1-minute public speaking

exposures. After every two exposures, participants will complete a rehearsal task where the participant is asked to use a positive or neutral approach to remember and recount the exposures they have just completed (for a total of approximately 60-90 minutes). Visit 2 will occur approximately 1 week after Visit 1 and will consist of another series of short 1-minute public speaking exposures, followed by the same rehearsal task after every two exposures. Participants will then be asked to complete another series of questionnaires (for a total of approximately 60-90 minutes) For the rehearsal task in Visits 1 and 2, participant will be randomized to practice rehearsing a) focusing on positive emotional aspects of the exposures, or b) focusing on neutral, factual aspects of the exposures. One week after Visit 2, participants will be asked to complete a brief set of questionnaires (approximately 5-10 minutes).

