After every two exposure trials, participants will then complete a rehearsal exercise (either positive or neutral rehearsal depending on their group assignment). Before the rehearsal exercise, participants will complete the visual analog scale to assess current mood. Participants will then be presented with instructions to complete a verbal rehearsal of the two exposures they just completed, followed by a written rehearsal of the two exposures they just completed. After the rehearsal exercise, participants will again rate their current mood using the visual analog scale, US expectancy ratings ("If you were to complete the same exact speech again, how likely is it that the feared outcome would occur?" where 0 = certain the feared outcome will not occur, 50 = completely uncertain, and 100 = certain the feared outcome will occur; and "Did the feared outcome occur?" where 0 = no, and 1 = yes), and relief ratings ("How relieved are you that the feared outcome did not occur?" where 0 = not at all, 50 = moderately, and 100 = very).

This entire process will be repeated four times, resulting in a total of 8 exposure practices and 4 rehearsal exercises. Participants will then complete a brief set of questionnaires including the LSAS, PRPSA, PVSS, and BAS. The visit is expected to take approximately 60-90 minutes to complete.

FOLLOW-UP

After completion of Visit 2, approximately one week later participants will be sent a short list of questionnaires to be completed independently. Surveys include the public anxiety screening questions, PRPSA, PVSS, and BAS and are expected to take 5-10 minutes to complete.

After completion of the follow-up surveys, participants will be compensated for their time one credit per hour of study participation. All participants will additionally be provided with a referral list at the end of the study.

Statistics & Data Analysis:

Sample size. The sample size will be 74 participants (37 per group). An a priori analysis using G*Power (Faul et al., 2007) indicated that a sample size of 74 would be sufficient to detect a significant effect based on a similar previous study ($d=.30$; Craske et al., 2019) with a power of .80 and an alpha of .05.

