Reward sensitivity and positive affect predicting relief. Linear mixed models will be utilized to assess whether baseline reward sensitivity, measured by the Positive Valence System Scale (PVSS, Khazanov et al., 2020) and the Behavioral Activation Scale (BAS, Carver & White, 1994), and positive affect, measured by a visual analog scale, predict relief rate over the course of exposures. Relief rate will be calculated using a computational model derived from the Rescorla-Wagner model (Rescorla & Wagner, 1972) to capture change in self-reported relief ratings over time. A linear mixed model will also be utilized to assess whether positive affect before an exposure trial predicts subsequent relief on the same trial.

Relief predicting learning rate. A linear mixed model will be utilized to assess whether relief after the first exposure trial predicts learning rate for subsequent exposure trials. Learning rate will be calculated using a computational model derived from the Rescorla-Wagner model (Rescorla & Wagner, 1972) to capture change in self-reported US expectancy ratings over time.

Comparison of positive and neutral rehearsal exercises. A repeated measures between-subjects ANOVA will be utilized to test whether participants in the positive rehearsal intervention show greater reductions in anxiety symptoms (public speaking anxiety screening questions; LSAS, Liebowitz, 1987; PRPSA, McCroskey, 1970) or greater increases in positive affect or reward sensitivity relative to participants in the neutral rehearsal intervention. We will use paired samples t-tests to test whether participants in the positive rehearsal intervention show a faster learning rate or relief rate relative to participants in the neutral rehearsal intervention.

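### The power of .80 at d = .30 is stated without the inputs that produce it; if d is a between-arm difference, the planned group x time test at 37 per group falls well short unless measurements correlate at about .9

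*Combined protocol and SAP*

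**What the plan says.** Statistics & Data Analysis, Sample size: "The sample size will be 74 participants (37 per group"). The paragraph names G*Power and says that "a sample size of 74 would be sufficient to detect a significant effect based on a similar previous study ($d=.30", "with a power of .80 and an alpha of .05". It gives nothing further about the calculation.

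Specific Aims: "The current study has three primary aims". The first two concern predictors of relief and of learning, and the third compares the rehearsal arms. The power statement is tied to none of them. For the third aim, "we hypothesize that the positive rehearsal group will lead to significantly greater reductions in symptoms of social phobia".

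The arm-comparison paragraph at the end of Statistics & Data Analysis sets the test for that aim: "A repeated measures between-subjects ANOVA will be utilized to test whether participants in the positive rehearsal intervention show greater reductions in anxiety symptoms". The same test is to look for "greater increases in positive affect or reward sensitivity relative to participants in the neutral rehearsal intervention". This paragraph is not linked to the power calculation either.

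Measurement schedule: the LSAS, PRPSA, PVSS and BAS are taken at Visit 1. At the end of Visit 2, "Participants will then complete a brief set of questionnaires including the LSAS, PRPSA, PVSS, and BAS". The follow-up survey repeats the PRPSA, PVSS and BAS but not the LSAS.

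**The concern.** A d of .30 is usually read as a difference of 0.30 SD between two groups. The allocation per group, the hypothesis about arms and the ANOVA with a between-subjects factor all point that way. On that reading, 37 per group looks far too few for power .80.

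The inputs left out also decide the answer. With f = .15, three measurements and N = 74, power runs from .655 at r = .3 to .996 at r = .8. A reader cannot check the claim without knowing which test, how many measurements and what correlation were entered.

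At stake is how a null arm comparison is read. If the stated .80 is taken at face value, a non-significant result may be treated as evidence against an effect of d = .30 that the test had little chance of finding.

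**Working it through.** **Inputs.** From the documents: N = 74, 37 per group, d = .30, alpha .05, target power .80; three measurements for PRPSA, PVSS and BAS, and two for LSAS. Assumed: equal variances and equal correlation r between measurements (compound symmetry), r from .3 to .8, no dropout.

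**Step 1: reproduce 74.** For a within-between interaction with two groups and m measurements, the noncentrality is lambda = f² x N x m / (1 - r), with m - 1 and (N - 2)(m - 1) degrees of freedom. Take f = d/2 = .15, m = 3, r = .5:

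- N = 74: lambda = .0225 x 74 x 3 / .5 = 9.99, power .806.
- N = 72: lambda = 9.72, power .795.

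So 74 is the smallest even total that reaches .80. These inputs are inferred and not unique: m = 2 with r = .59 gives .803.

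**Step 2: what f = .15 means as an arm difference.** If the arms differ by delta_t SD at measurement t, then f² = (1/m) x sum of [(delta_t - mean delta)/2]².

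- Two measurements, pattern (0, d): f² = d²/16, so f = d/4, and f = .15 means d = 0.60.
- Three measurements, difference at both post-baseline points (0, d, d): f² = d²/18, so d = .15 x √18 = 0.64.
- Three measurements, gradual (0, d/2, d): f² = d²/24, so d = .15 x √24 = 0.73.

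Conversely, an arm difference of 0.30 SD gives f = .075, .071 and .061, about half of .15 or less.

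**Step 3: power for an arm difference of 0.30 SD.** At r = .5, lambda is 1.665 (two measurements: .075² x 74 x 2 / .5), 2.22 (three, both post points) and 1.665 (three, gradual). Over the assumed correlations:

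| r | Two measurements | Three (0, d, d) | Three (0, d/2, d) |
|---|---|---|---|
| .3 | .19 | .18 | .15 |
| .5 | .25 | .24 | .19 |
| .7 | .38 | .38 | .29 |
| .8 | .52 | .54 | .42 |
| r needed for .80 | .90 | .89 | .915 |

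**Step 4: arm difference detectable with 80% power at 37 per group (SD units).**

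| r | Two measurements | Three (0, d, d) | Three (0, d/2, d) |
|---|---|---|---|
| .3 | 0.78 | 0.75 | 0.86 |
| .5 | 0.66 | 0.63 | 0.73 |
| .7 | 0.51 | 0.49 | 0.56 |
| .8 | 0.42 | 0.40 | 0.46 |

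**Step 5: a more focused test.** A single contrast of the mean of the two post-baseline values minus baseline has variance 1.5(1 - r), so its standardised effect is .30/√(1.5(1 - r)). When the difference is present at both post-baseline points, two-sided power is .24, .31, .48 and .64 at r = .3, .5, .7 and .8.

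**Step 6: one input cannot fit every outcome.** LSAS has two measurements. Even granting f = .15 and r = .5, lambda = .0225 x 74 x 2 / .5 = 6.66 and power is .72; 90 participants would be needed for .80. The affect scale can be rated up to 18 times (1 at the Visit 1 baseline, 8 around the four rehearsals, 1 at the start of Visit 2, 8 more), and the plan does not say which ratings enter the ANOVA.

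**The case against.** The strongest reply is that nothing is miscalculated. The inputs that give 74 match the planned ANOVA and the three occasions of the PRPSA, PVSS and BAS. A reader might infer from Step 3 that 74 is an arithmetic error; the documents do not support that, and Step 1 points the other way. What stands against the plan is that the inputs are not given, and that on this route the effect being powered is about twice d or more when read as an arm difference.

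Second, d = .30 comes from a prior study and its meaning is not stated. It could be a change within persons. A one-sided paired test on all 74 would have power .82 at d = .30 (two-sided .72). Such a test does not compare two independent arms, although the plan does name paired t-tests for comparing learning and relief rates between arms. This objection stands: the shortfall is conditional on what d describes.

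Third, the ceiling of r = .8 is an assumption. Measurements are about a week apart and a higher correlation cannot be excluded. At r = .9 the F test gives .81 (two measurements), .85 (three, both post points) and .73 (three, gradual). The hypothesis is also directional: a one-sided version of the Step 5 contrast gives .43 at r = .5 and .76 at r = .8, and reaches .80 at r of about .82. This also stands, so .15 to .54 must not be read as the power of the trial under every analysis. It belongs to the two-sided group x time F test on two or three measurements with r from .3 to .8.

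**Conclusion.** The concern holds in conditional form.

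- **High confidence:** the power statement omits the inputs needed to check it. If 74 came from f = d/2 = .15, the effect powered for is an arm difference of about 0.60, 0.64 or 0.73 SD, depending on the number and pattern of measurements, not 0.30 SD.
- **Moderate confidence:** the stated .80 does not hold for the arm comparison. This requires d = .30 to be a between-arm difference in raw SD units, and r below about .89 to .92 for the group x time test. Under those conditions, at r = .5 a true difference of 0.30 SD would be missed at least three times in four; at r = .8 it would be missed roughly half the time.

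A reader might go further and conclude that the trial is simply underpowered. The documents do not support that: they give neither the meaning of d nor the correlation. For LSAS the claim is weak even on the favourable route, at .72 with r = .5.

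**What to change.** Keep N = 74. In the sample-size paragraph, state the G*Power test, f and how it was obtained from d, the number of measurements, the correlation, the sidedness where a t-test is meant, what d describes, and which of the three aims the calculation serves.

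If d is a between-arm difference, replace the .80 claim with text such as:

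> With 37 per group and two-sided alpha .05, assuming compound symmetry and a difference present at every post-baseline measurement, the group x time test on outcomes measured two or three times has 80% power for an arm difference of about 0.75-0.78 SD at correlation .3, 0.63-0.66 at .5, 0.49-0.51 at .7 and 0.40-0.42 at .8. The detectable difference is larger if the effect builds up gradually. These figures do not cover the repeated affect ratings or the comparisons of learning rate and relief rate.

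If d is not a between-arm difference, say so and give the detectable arm difference separately, with the same limits. In either case, report arm effects with confidence intervals, and do not read a non-significant result as absence of an effect of d = .30.

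The cost is wording only, with no added participants or visits. The downside is that the stated power becomes less favourable.

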There is also promising evidence which suggests that reward processes may facilitate extinction learning, though studies have yet to be conducted in a clinical sample. Experimental studies have demonstrated that greater relief, a positive emotion that occurs following US omission, is associated with greater expectancy violation (San Martín et al., 2020; Vervliet et al., 2017; Willems & Vervliet, 2021). This suggests that positive emotions during exposure (e.g., relief) may directly influence the extinction learning process. Reduced positive affect has been associated with decreased updating of US expectancies, leading to slower learning during extinction (Young et al., 2021). In contrast, elevated positive affect has been associated with enhanced encoding, rehearsal, and retrieval processes, which may lead to faster learning during extinction and prevent return of fear (i.e., relapse) (Zbozinek & Craske, 2017). Strategies designed to enhance reward sensitivity and positive affect may therefore be an important avenue of future research to improve exposure therapy outcomes. While not yet applied during exposure, strategies aimed to increase reward sensitivity via positive-focused rehearsal have led to decreased anxiety, depression, and negative affect and increased positive affect (Chen et al., 2021; Craske et al., 2019, *in press*; A. Waters et al., 2016; L. Waters & Stokes, 2015). Recent work has shown that rehearsal without a positive focus immediately following exposure leads to reductions in anxiety (McGlade & Craske, 2021). Therefore, rehearsal following exposure that specifically focuses on positive emotions to increase reward sensitivity has the potential to lead to even greater symptom improvement.

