Thus, the current study seeks to examine the role of relief during extinction learning and to test whether positive-focused rehearsal exercise may be implemented to improve treatment outcomes in exposure therapy in a population of individuals who demonstrate excessive fear of public speaking. There are three main goals of the study: 1) examine whether baseline reward sensitivity and positive affect predict relief following exposure, 2) examine whether relief predicts subsequent extinction learning across exposure trials., and 3) test the efficacy of a positive rehearsal exercise following exposure compared to a neutral rehearsal exercise. Participants will be randomized to either complete positive or neutral rehearsal exercises following exposure. Prior research has shown that mental rehearsal following exposure enhances treatment results (McGlade & Craske, 2021). Thus, all participants are expected to see positive results following exposure and rehearsal exercises, but participants who complete positive rehearsal exercises are expected to exhibit greater reward sensitivity and positive affect, thereby strengthening their learning of the new inhibitory association and exhibiting greater treatment effects.

Specific Aims:

The overall aim of this research is to evaluate methods for enhancing the effectiveness of exposure therapy for the treatment of anxiety disorders, and to better understand reward and relief mechanisms as they relate to extinction learning during exposure. Exposure therapy is an

extinction-based behavioral technique, often employed in the context of cognitive behavioral therapy (CBT). It involves strategically exposing a participant to a feared stimulus in an effort to generate new non-fear associations with that stimulus. Importantly, across anxiety disorders, treatment response rates for CBT average approximately 50% post-treatment and at follow-up, indicating a need for more effective treatment methodology (Loerinc et al., 2015).

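### The same-trial affect–relief model in Aim 1 specifies no exposure, visit or group term, so if affect and relief both drift over trials it can create, mask or reverse the association being tested

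*Combined protocol and SAP*

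**What the plan says.** The analysis is described under Statistics & Data Analysis, in the paragraph on reward sensitivity and positive affect predicting relief: "A linear mixed model will also be utilized to assess whether positive affect before an exposure trial predicts subsequent relief on the same trial". That sentence gives the predictor, the outcome and the model class. No other fixed effect and no random effect is stated, and no other section adds one.

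The hypothesis it serves is in Specific Aims, stated as holding in both rehearsal groups: "lower positive affect will be associated with lower subsequent relief ratings relative to higher positive affect".

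Three other statements bear on time:

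- **Relief.** Specific Aims defines "relief rate (change in relief ratings across exposure trials" as a study quantity and predicts that it will differ between the rehearsal groups. Background & Significance adds that "greater relief, a positive emotion that occurs following US omission, is associated with greater expectancy violation". Neither gives a direction or size for the trend in relief.
- **Affect.** Background & Significance says "participants who complete positive rehearsal exercises are expected to exhibit greater reward sensitivity and positive affect", and Specific Aims predicts for that group "greater increases in reward sensitivity and positive affect at the end of the study". No size is given.
- **Design.** Each visit has a cycle of two exposures and one rehearsal, "resulting in a total of 8 exposure practices and 4 rehearsal exercises", so there are 16 exposures over two visits. Affect is rated before the first exposure and around each rehearsal. A fresh rating therefore precedes exposures 1, 3, 5 and 7 of a visit, and none falls between the two exposures of a pair.

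**The concern.** Two series that both move with trial number are correlated within a person even when affect on a given trial has no bearing on relief on that trial. A participant random intercept does not remove this, because it absorbs differences between people and not a course over time that people share. A group main effect does not remove it either.

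The sign of the error depends on the direction of the trends. If affect and relief both rise, the hypothesised positive association can appear with no trial-level link. If relief falls while affect rises, a true positive association is hidden or turns negative. The plan's link between relief and expectancy violation leaves the second case open, since expectancy may fall as extinction proceeds. The direction cannot be known beforehand, so neither a significant nor a null result could be read with confidence.

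**Working it through.** **Figure in the plan.** There is none for this model. The only computed figure is N = 74. It can be reproduced as a within-between interaction with f = 0.30/2 = 0.15, three measurements and correlation 0.5 (power 0.806); the last two inputs are assumptions. It does not bear on this point.

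**Closed form for the spurious slope.** From the documents: 74 participants and T = 16 trials. Assumed: person SD = within-person SD = 1 for both variables; k = 8 affect ratings, each carried over its pair of trials; linear drifts of δa (affect) and δr (relief) over the 16 trials; true slope 0; random-intercept model.

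- Variance of the stepped trial shape: v = (2/15)² × (8² − 1)/12 = 0.0933.
- Slope ≈ T·δa·δr·v / [T((k−1)/k + δa²v) + T(1 + 1/k)/(1 + T)].
- δa = δr = 1.0: 1.493 / (15.493 + 1.059) = 0.090 (simulated 0.089).
- δa = δr = 0.5: 0.373 / (14.373 + 1.059) = 0.024 (simulated 0.024).
- δa = δr = 0.3: 0.134 / (14.134 + 1.059) = 0.009 (simulated 0.009).

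The slope scales with the product δa·δr, so it is zero if either variable is flat.

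**Rejection rates with no true link** (500 simulated trials per row, two-sided 0.05):

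| Drift, affect / relief (SD) | No time term | Trial as factor |
|---|---|---|
| 0 / 0 | 5.2% | 4.6% |
| 1.0 / 0 | 5.6% | 5.4% |
| 0 / 1.0 | 4.6% | 5.0% |
| 0.3 / 0.3 | 7.2% | 4.6% |
| 0.5 / 0.5 | 13.8% | 4.8% |
| 1.0 / 1.0 | 84.0% | 4.4% |
| 1.0 / −1.0 | 84.6%, all negative | 4.8% |

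Using only the 8 trials that directly follow an affect rating, the rate without a time term is 10.6% at 0.5 SD and 64.2% at 1.0 SD.

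**Masking.** With a true slope of 0.10 and no drift, power is 93.6%. With affect +1.0 SD and relief −1.0 SD, the estimated slope shrinks to 0.01 and power to 7.4%. Trial as a factor restores a slope of 0.10 and power of 92.0%.

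**Shape of the time term.** With curved drifts of 1.0 SD in both variables, a linear trial term still leaves 11.0% false positives, against 5.6% with trial as a factor.

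**On the rating scales.** Assumed: relief SD 15 between and 15 within person; affect SD 1.3 between and 1.2 within; exposures 1, 3, 5 and 7 of two visits; drift within each visit; no true link. Ranges reflect repeated runs.

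| Affect drift | Relief drift | No time term |
|---|---|---|
| +1, both arms | −20 | 66–74% |
| +1, both arms | +20 | 63–65% |
| +1, both arms | −10 | 24–26% |
| +0.5, both arms | −20 | about 25% |
| +0.5, both arms | −10 | about 10% |
| +0.5, both arms | −5 | about 6% |
| +1, positive arm only | ±20, both arms | 21–25% |
| +1, positive arm only | −10, both arms | about 11% |

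These rows spread the drift over exposures 1 to 8. If it is complete by exposure 7, the rate for affect rising in the positive arm only and relief moving 20 points is about 35%. Adding a group main effect leaves these rates essentially unchanged. Exposure-by-visit as a factor brings them to about 5%.

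**Drift confined to one arm in both variables.** If affect (+1) and relief (±20) both move only in the positive arm, exposure-by-visit as a factor alone still rejects in about 17–18% (10–13% if the drift is spread over exposures 1 to 8). Adding group-by-exposure/visit terms brings it to about 5%.

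**The case against.** The plan gives each model one sentence and lists no covariates or random effects for any of them. A reader might infer that time has been deliberately excluded. The documents support only that no time term is specified. This stands as a limit on the wording, but the omission still leaves a choice that can change the result open until the data are seen.

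A reader might also infer that the exposures are meant to move both variables in both arms, citing "all participants are expected to see positive results following exposure and rehearsal exercises". In context that sentence concerns treatment benefit, and it goes on to single out the positive arm for affect. A rise in affect in the neutral arm is therefore an assumption. This objection stands and lowers the plausible size of the bias, but does not remove it, as the rows with affect rising in one arm show.

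Defining a relief rate does not predict a common trend of known direction, and small drifts do little harm. Both points stand, and for that reason the high percentages should not be quoted alone.

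Finally, time and group-by-time terms discard affect variation shared by everyone in an arm at a given exposure, some of which could truly act on relief. That variation cannot be separated from the passage of time, so little usable information is lost. With no drift and a true slope of 0.10, power is 93.2% with the trial factor and 93.6% without.

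**Conclusion.** The concern holds in a limited form. As specified, the same-trial model has no protection against a time course shared by affect and relief, and the plan gives reasons to expect movement in both. Whether that matters in this trial depends on drift sizes and SDs that the documents do not give:

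- near-nominal false-positive rates (about 6–7%) for small drifts of about 0.3 SD in both variables;
- about 10–25% for moderate drifts;
- about 20–35% if affect rises 1 point only in the positive arm while relief moves 20 points;
- over 60% for large drifts in both arms;
- no inflation if only one variable drifts.

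A reader might infer that all of Aim 1 is compromised. It is not. The relief-rate models use baseline predictors of a summary that already captures change over trials, and the between-group comparisons do not use this model. The plan should be amended on this point, but it is not a fatal flaw.

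**What to change.** In the Statistics & Data Analysis paragraph on reward sensitivity and positive affect predicting relief, write out the same-trial model in full:

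- **Fixed effects for time:** exposure number within visit as a factor, visit, and their interaction.
- **Fixed effects for arm:** group, and its interactions with the exposure and visit terms. The plan expects both affect gains and relief rate to differ by arm.
- **Affect:** the deviation from the participant's own mean, plus that mean, with the hypothesis tested on the deviation. The split complements the time terms and does not replace them, because centring alone leaves a common trend in place.
- **Random effect:** participant.
- **Rows used:** state whether only exposures with a fresh affect rating enter, or whether ratings are carried over to the second exposure of each pair.

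The cost is SAP wording and no new data. With the freshly rated exposures only, 4 exposures × 2 visits × 2 groups = 16 cells, so 15 degrees of freedom out of 74 × 8 = 592 observations. With all exposures it is 31 out of 74 × 16 = 1,184, before any missing data.
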